### **Zero or Missing Baseline Values when Calculating Percent Change from Baseline**

When baseline value is missing for a subject, percent change from baseline cannot be calculated and therefore percent change values will be set to missing in these situations. When the baseline value is 0, the percent change will be set to missing, except when the post baseline value is also 0, in which case the percent change will be set to 0.

### **Definition of Final Observation for Safety Analysis**

**Period 1:** The final observation is defined as the last non-missing observation collected

- within 30 days following the last dose of study drug in Period 1 for subjects who discontinued from the study drug without having any dose of study drug in Period 2,
- on or before the day of the first dose of study drug in Period 2 for subjects who had at least one dose of the study drug in Period 2.

Laboratory and vital sign evaluations performed on the day of the first dose of study drug in Period 2 will be included in the analysis for Period 1. AEs with onset on the date of the first dose of Period 2 will be attributed to Period 1.

**Period 2:** The final Observation in each period is defined as the last non-missing observation collected within 30 days following the last dose of study drug in the respective period.

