Period 2 will begin after the Week 16 Visit and will end at the Week 88 Visit. At the Week 16 Visit, subjects will be re-randomized as described in Section 5.1. During Period 2 of the study, subjects will visit the study site at Weeks 20, 24, 32, 40, 52, 64, 76, and 88. A \pm 5 day window is permitted around scheduled study visits. Subjects will start on their assigned treatment at the Week 16 visit.

The last dose of study drug is taken the day prior to the Week 88 visit.

Twice daily use of an additive-free, bland emollient is required throughout Period 2.

Discontinuation of Study Drug and Continuation of Study Participation

Subjects may discontinue study drug treatment, but may choose to continue to participate in the study (refer to Section 5.4.1 for additional details). Subjects who prematurely discontinue study drug should complete a Premature Discontinuation Visit (PD visit) as soon as possible, preferably within 2 weeks. Afterwards, subjects should follow the regular visit schedule as outlined in Table 2 and adhere to all study procedures except for dispensing study drug, PK sample collection, and blood and skin biopsy sample collection for optional exploratory research and validation studies. In addition, all future rescue and efficacy-driven discontinuation criteria no longer apply.

In Period 1, discontinuation from study drug will be mandatory for any subject with an EASI score worsening of 25% or more compared with their Baseline EASI score at any 2 consecutive scheduled study visits from Week 4 to Week 12.

In Period 2, discontinuation from study drug will be mandatory for subjects with < EASI 50 response compared with their Baseline EASI score 4 weeks following rescue with topical corticosteroids or at any visit thereafter.

Premature Discontinuation of Study (Withdrawal of Informed Consent)

Subjects may withdraw from the study completely (withdrawal of informed consent) for any reason at any time (refer to Section 5.4.2 for additional details). If a subject prematurely discontinues study participation (withdrawal of informed consent), the procedures outlined for the Premature Discontinuation visit (PD visit) should be completed as soon as possible, preferably within 2 weeks of study drug discontinuation. In addition, if the subject is willing, a 30-day follow-up visit (or phone call if a visit is not possible) may occur to determine the status of any ongoing AEs/SAEs or the occurrence of any new AEs/SAEs.

Follow-Up Period

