#### **4.2 Design Diagram**

This is an 88-week Phase 2b, randomized, double-blind, parallel-group, placebo-controlled multicenter study of safety and efficacy of upadacitinib in adult subjects with moderate to severe AD.

The duration of the study will be up to 88 weeks and will include a 35-day maximum screening period, a 16-week double-blind treatment period (Period 1) and a 72-week double-blind treatment period (Period 2). In addition, a 30-day follow-up visit (or phone

---

call if a visit is not possible) should occur to determine the status of any ongoing AEs or serious adverse events (SAEs), or the occurrence of any new AEs/SAEs.

**Period 1:** A 16-week double-blind, placebo-controlled treatment period during which subjects will be randomized in a 1:1:1:1 ratio to one of four treatment groups:

- Group 1: upadacitinib 7.5 mg once daily (QD) for 16 weeks
- Group 2: upadacitinib 15 mg QD for 16 weeks
- Group 3: upadacitinib 30 mg QD for 16 weeks
- Group 4: Matching Placebo for 16 weeks

Randomization will be stratified by geographic region (US/PR/Canada, EU/AUS, and Japan). Enrollment in Japan will be capped at 10% of subjects (4 subjects per group).

In Period 1, discontinuation from study drug will be mandatory for any subject with an Eczema Area and Severity Index (EASI) score worsening of 25% or more compared with their baseline EASI score at any 2 consecutive scheduled study visits from Week 4 to Week 12.

**Period 2:** a 72-week double-blind, placebo controlled treatment period during which subjects who complete Period 1 will be re-randomized at Week 16 within their original treatment group assignments to either upadacitinib or placebo into a 72-week double-blind, placebo controlled treatment period in a 1:1 ratio as shown in [Figure 1](#) (study design). Randomization will be stratified by geographic region and the improvement of EASI score by at least 75% (EASI 75 response) at Week 16. At the Week 16 visit, all subjects will be re-randomized as follows into Period 2:

- Group 1 in Period 1: upadacitinib 7.5 mg QD or matching placebo for 72 weeks
  - Group 2 in Period 1: upadacitinib 15 mg QD or matching placebo for 72 weeks
  - Group 3 in Period 1: upadacitinib 30 mg QD or matching placebo for 72 weeks
-

- Group 4 in Period 1: upadacitinib 30 mg QD or matching placebo for 72 weeks

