### **11.2.1 Treatment-Emergent Adverse Events**

A treatment-emergent Adverse Event (TEAE) is defined as an adverse event with an onset or worsening date that is on or after the first dose of study drug, and no more than 30 days after the last dose of study drug.

AEs where the onset date is the same as the study drug start date are assumed to be treatment-emergent. If an incomplete onset date was collected for an adverse event, the event will be assumed to be treatment-emergent unless there is other evidence that confirms that the event was not treatment-emergent (e.g., the event end date was prior to the study drug start date).

TEAEs for the safety population in each period are defined as an event with a start date on or after the date of first study drug dose in each period and up to 30 days after the last dose of study drug in the analysis period, or prior to the date of first dose in the subsequent period for subjects who entered in to the subsequent period.

Adverse event data will be coded using the Medical Dictionary for Drug Regulatory Activities (MedDRA) version 20.0 or most up to date version.

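### SAP 6.0 and SAP 11.2.1 assign an adverse event that starts on the day of the first Period 2 dose to different periods

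*SAP*

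**What the plan says.** Two places in the SAP set the boundary between periods for AEs.

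- **SAP 6.0, Definition of Final Observation for Safety Analysis:** "AEs with onset on the date of the first dose of Period 2 will be attributed to Period 1". The sentence before it places other safety data from that day in Period 1 as well: "Laboratory and vital sign evaluations performed on the day of the first dose of study drug in Period 2 will be included in the analysis".
- **SAP 11.2.1, Treatment-Emergent Adverse Events:** the window opens on the day dosing begins in the period concerned: "TEAEs for the safety population in each period are defined as an event with a start date on or after the date of first study". It runs to 30 days after the period's last dose, or "prior to the date of first dose in the subsequent period for subjects who entered in to the subsequent period". The same section adds a general convention: "AEs where the onset date is the same as the study drug start date are assumed to be treatment-emergent".

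On timing, Protocol 5.1 says of Period 2: "Subjects will start on their assigned treatment at the Week 16 visit". SAP 11.2 summarises treatment-emergent events by period, so the boundary decides which table counts the event. SAP 12.1, which lists departures from the protocol, does not mention the boundary, and no text ranks 6.0 above 11.2.1 or the reverse.

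**The concern.** The disputed day is normally a full safety visit. Protocol Table 2 schedules AE assessment, laboratory tests, vital signs, physical examination and ECG at Week 16. Protocol 5.3.1.1 requires blood to be drawn ahead of any dosing at a visit, so an abnormality in that sample reflects Period 1 treatment when the first Period 2 dose is taken afterwards. Several AEs of special interest in Protocol 6.1.1.3 rest on laboratory values (CPK elevation, anemia, neutropenia, decreased lymphocyte counts).

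If 11.2.1 is the rule programmed, an AE found at that visit before the new drug is taken is charged to the Period 2 arm, while its laboratory value is analysed in Period 1 under 6.0. If the Period 1 output is programmed from one section and the Period 2 output from the other, the event appears in both or in neither. That risk is practical, because the Period 1 analysis is run first, after its own database lock (Protocol 8.1.7).

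**Working it through.** The plan gives no figure to reproduce on this point. The check is to apply both rules to the same dates and then size the arms.

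**Inputs**
- Date rules: SAP 6.0 and SAP 11.2.1, as quoted.
- First Period 2 dose day, D: set to Day 113 for illustration, the nominal Week 16 day in SAP Table 2 (analysis windows).
- Eight treatment sequences: SAP Table 1 (treatment group notation).
- About 160 subjects in four equal groups (SAP 4.3), then 1:1 re-randomisation within group (SAP 4.2).

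**Step 1: the two rules**
- SAP 6.0: Period 1 if onset ≤ D and, by implication, Period 2 if onset > D.
- SAP 11.2.1: Period 1 if Day 1 ≤ onset < D; Period 2 if onset ≥ D.

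| AE onset | SAP 6.0 | SAP 11.2.1 |
|---|---|---|
| Day 112 | Period 1 | Period 1 |
| Day 113 (= D) | Period 1 | Period 2 |
| Day 114 | Period 2 | Period 2 |

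The rules differ on exactly one day. Reading the alternative end-points of the 11.2.1 window loosely does not help: its start-point alone still puts a Day 113 event in Period 2.

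**Step 2: mixed programming of a Day 113 event**
- Period 1 output by 6.0, Period 2 output by 11.2.1: counted in both.
- Period 1 output by 11.2.1, Period 2 output by 6.0: counted in neither.

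**Step 3: where the treatment label changes**
Treatment differs between periods in 7.5 mg/placebo, 15 mg/placebo, 30 mg/placebo and placebo/30 mg, which is 4 of 8 sequences. With 1:1 re-randomisation that is about half of those entering Period 2: 160 × 4/8 = 80 at most, if everyone completed Period 1. In the other four sequences only the period changes.

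**Step 4: weight of one subject**
- Period 2 arm: 160/8 = 20 at most, so one subject is 1/20 = 5 percentage points.
- Period 1 arm: 160/4 = 40, so one subject is 1/40 = 2.5 percentage points.

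SAP 11.2.1.2 counts a subject once per category, so the full 5 points applies only if that subject has no other Period 2 event in the category.

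**Step 5: effect on the rate denominators**
SAP 9.1 caps Period 1 exposure for continuing subjects at D minus the first dose date, here 113 − 1 = 112 days. Day D is counted in Period 2 exposure. Assigning Day D events to Period 1 therefore puts them one day outside their denominator. One day in 112 is 0.9%, which is negligible but should be stated.

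**The case against.** The best opposing case is that the contradiction is real but the consequence is narrow.

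- **Only AE records are affected.** Laboratory values and vital signs on that day stay in Period 1 under SAP 6.0, and the footnote to SAP Table 2 lets the Week 16 window include the day of the first Period 2 dose. Mean changes, toxicity-grade shifts and liver screening do not depend on the AE boundary. This stands.
- **The first Period 2 dose may not fall on the visit day.** Protocol 5.3.2.1 lets subjects keep their usual dosing time away from the clinic at visits other than Weeks 2 and 4. If the first Period 2 dose is taken the next day, both rules put a Week 16 AE in Period 1. This stands, and reduces the number affected.
- **Laboratory AEs need not carry the visit date.** The documents give no convention for dating their onset. Protocol 6.1.1.1 makes an abnormality an AE only under stated conditions, and many entries in Protocol Table 6 require a repeat sample. This stands.
- **Little inference depends on it.** Protocol 8.1 makes Period 2 summaries descriptive, SAP 11.1 tests laboratory and vital-sign changes rather than AEs, and rates for AEs of special interest are also given for both periods combined, where the period boundary alone removes nothing. This stands, but it does not repair the by-period tables.

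A reader might infer that Week 16 findings in general move to the wrong treatment, or that a material number of subjects change period. The documents do not support either. The first fails because laboratory and vital-sign data are assigned consistently and half the sequences keep the same treatment. The second needs a Week 16 onset rate and a number entering Period 2, and the documents give neither.

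Nor is every error in one direction. A date-only rule following 6.0 charges a reaction that begins after the first Period 2 dose that day to the Period 1 treatment.

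**Conclusion.** The two sections conflict for AEs with onset on the first Period 2 dose date. As written, the by-period AE tables cannot be programmed reproducibly. The reach is AE records only, one day per subject, with a change of treatment label confined to the four switching sequences.

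The number of such events is unknown and probably small. The 5-point figure is the weight of one subject in a Period 2 arm of 20. It assumes all 160 subjects enter Period 2 in equal arms and that the subject has no other event in the category; a smaller arm would give one subject more weight. No primary or inferential efficacy result is touched. The point is still worth correcting, because a single AE of special interest is visible in arms of this size and the remedy is cheap.

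**What to change.** Amend SAP 11.2.1 to agree with SAP 6.0. For subjects who continue, Period 1 events would be those with onset up to and including the date of the first Period 2 dose, and Period 2 events those with onset after it. This direction keeps an AE in the same period as that day's laboratory value and vital signs. Limit the same-day convention in 11.2.1 to the first dose of the study, so that it does not reopen the question at Week 16.

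Where AE onset time relative to the dose is collected, use it to assign same-day events. Protocol 6.1 mentions only the onset date, so availability of a time should be checked first. Apply the same boundary to the by-dose summaries across periods (SAP 11.2) and the event rates (SAP 11.2.1.7), noting the one-day mismatch with the exposure definition in SAP 9.1.

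The cost is a sentence in 11.2.1 and short cross-references in the other sections, with no new data collection. The downside is that, without onset times, an AE starting after the first Period 2 dose on that day is counted in Period 1.

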### **Definition of Rx Days (Days Relative to the First Dose of Study Drug)**

Rx days are calculated for each time point relative to the date of first dose of study drug. They are defined as the number of days between the day of the first dose of study drug and the specific time point. Rx days are negative values when the time point of interest is prior to the first study drug dose day. Rx days are positive values when the time point of interest is on or after the first study drug dose day. The day of the first dose of study drug is defined as Rx Day 1, while the day prior to the first study drug dose is defined as Rx Day -1 (there is no Rx Day 0).

---

For analysis in Period 1 (P1 Rx Day) and Period 2 (P2 Rx Day), the Rx Day is calculated relative to the first dose of study drug in Period 1 and Period 2, respectively.

For subjects randomized but not dosed, Rx Days are calculated relative to the randomization.

### **Definition of Analysis Windows**

All time points and corresponding time windows in Periods 1 and 2 are defined based on P1 Rx Days P1 and P2 Rx Day, respectively.

Analysis time windows are constructed using the following algorithm:

- Determine the nominal Rx Day for each scheduled visit (e.g., Week 4 [4 weeks after baseline visit] equals P1 Rx Day 29).
- In order to include all post baseline data, the first post-baseline interval starts on the first day after the first dose of study drug (P1 or P2 Rx Day 2).
- Determine the window around a specific nominal Rx Day by adding or subtracting half of the interval between adjacent visits (e.g., days between Week 2 and Week 4 is 14). The threshold between adjacent visits is determined by splitting the interval evenly between the visits. If the resulting split is between Rx days, then the threshold is determined as the midpoint between the adjacent visits. If the resulting split is on an Rx day, then the threshold is determined as being between that Rx day and the Rx day prior to it (e.g., the split between Week 2 and Week 4 would be between P1 Rx Days 22 and 23).
- If more than one assessment is included in a time window, the assessment closest to the nominal day will be used. If there are two observations equidistant to the nominal day, the one after the nominal day will be used in analyses. If more than one assessment is included on the same day, then the worst assessment on that day will be used in analyses, except otherwise specified.

For subjects randomized but not dosed, Rx Day calculated relative to Randomization in each period.

For the efficacy variables, vital signs, and laboratory values, visit windows are defined as follows.

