Subjects who complete Period 1 will be re-randomized at Week 16 within their original treatment group assignment to either ABT-494 (upadacitinib) or placebo into a 72-week double-blind, placebo controlled treatment period (Period 2) in a 1:1 ratio as shown in [Figure 1](#) (study design). Randomization will be stratified by geographic region and EASI 75 response at Week 16. At the Week 16 visit, all subjects will be re-randomized as follows into Period 2:

- Subjects from Group 1 in Period 1: ABT-494 7.5 mg QD or matching placebo for 24 weeks
- Subjects from Group 2 in Period 1: ABT-494 15 mg QD or matching placebo for 24 weeks
- Subjects from Group 3 in Period 1: ABT-494 30 mg QD or matching placebo for 24 weeks
- Subjects from Group 4 in Period 1: ABT-494 30 mg QD or matching placebo for 24 weeks

[figure not shown]
For subjects re-randomized to placebo, ABT-494 7.5 mg QD or ABT-494 15 mg QD in Period 2, blinded rescue therapy with ABT-494 30 mg QD will be provided after the first instance of a < EASI 50 response starting at the Week 20 visit (4 weeks after re-randomization into Period 2). These subjects will continue on ABT-494 30 mg QD for the remainder of the study.

During Period 2, concomitant class III – IV, medium potency topical corticosteroid treatment will be permitted at the Week 24 visit and thereafter in subjects after a second instance of < EASI 50 response in any two Period 2 study visits beginning from Week 20 (see Section 5.2.3.4 for permitted treatments). For subjects who receive topical corticosteroid rescue therapy, an additional visit will be required 4 weeks later. Discontinuation from study drug will be mandatory for subjects with < EASI 50 response compared with their Baseline EASI score 4 weeks following rescue with topical corticosteroids or at any visit thereafter.

In order to minimize missing data for efficacy and safety assessments, subjects who prematurely discontinue study drug treatment should continue to be followed for all regularly scheduled visits, unless they have decided to discontinue the study participation entirely (withdrawal of informed consent).

A schematic of the overall study design is shown in [Figure 1](#).

Figure 1. Study Design

Screening Period

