Starting at the Week 20 visit (4 weeks after re-randomization into Period 2), rescue therapy with upadacitinib 30 mg QD will be provided to subjects who have a first instance of an EASI score improvement of less than 50% (i.e., < EASI 50 response), when compared against the Baseline. These subjects will continue on upadacitinib 30 mg QD for the remainder of the study.

[figure not shown]
During Period 2, concomitant class III – IV, medium potency topical corticosteroid treatment will be permitted at the Week 24 visit and thereafter in subjects after a second instance of < EASI 50 response in any two Period 2 study visits beginning from Week 20 (see Protocol Section 5.2.3.4 for permitted treatments). For subjects who receive topical corticosteroid rescue therapy, a visit will be required 4 weeks after receiving the rescue therapy. Discontinuation from study drug will be mandatory for subjects with < EASI 50 response compared with their baseline EASI score 4 weeks following rescue with topical corticosteroids or at any visit thereafter.

In order to minimize missing data for efficacy and safety assessments, subjects who prematurely discontinue study drug should continue to be followed for all regularly scheduled visits, unless they have decided to discontinue the study participation entirely (withdrawal of informed consent).

A schematic of the overall study design is shown in [Figure 1](#).

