### 10.1.5 Missing Data Imputation

Missing data will be imputed using the following methods for the efficacy analyses:

- Non-Responder Imputation (NRI): the NRI analysis will categorize any subject who does not have evaluation during a specific visit window as a non-responder for that visit. The exception is when the subject is a responder both before and after a specific visit window, in which case the subject will be categorized as a responder for the visit. Only observations within the same analysis period will be used. The NRI will be the primary approach in the analyses of categorical variables.

- Last Observation Carried Forward (LOCF): The LOCF analyses will carry forward the most recent previous non-missing value (last completed non-missing value, for composite endpoint) to impute missing data at later visits in the same period. Baseline efficacy evaluations will not be carried forward. LOCF will be the primary approach in the analyses of continuous variables, and the secondary approach in the analysis of categorical variables.
- As-Observed Cases (OC): The as-observed analysis will not impute values for missing evaluations, and thus a subject who does not have an evaluation on a scheduled visit will be excluded from the as-observed analysis for that visit. As-observed analysis will be the secondary approach in the analysis of continuous variables.
- Multiple Imputation (MI): The MI approach will be used for sensitivity analyses on the Week 16 endpoints of EASI percent change from Baseline, EASI 75, and the Investigator Global Assessment (IGA) response of 0 (clear) or 1 (almost clear). If MI is not applicable due to the nature of the data (e.g., MCMC algorithm does not converge), logistic regression or mixed effect model repeat measurement (MMRM) methods will be applied as the sensitivity approach, whichever applicable.

The Multiple Imputation analysis will be carried out in three steps.

- Imputation of missing data. The imputation will be generated for each efficacy endpoint measurement. The variables to be included in the imputation model are: Baseline EASI (or IGA), treatment group, and measurements at each visit up to the end of the analysis period. For each endpoint, 20 'complete' datasets will be generated using SAS PROC MI. The imputed post-baseline measurements will be rounded to the same precision as the observed data before the determination of responder status (e.g., EASI 75 and EASI percentage change from Baseline).

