## 10.5 Exploratory Variables

The following endpoints will be analyzed at all visits or weeks that the assessments are collected, except for daily assessments where results based on a rolling average by week will be presented.

- Time to EASI 50/75/90 and IGA "0" or "1" response in Period 1.
  - Proportion of subjects achieving EASI 50/75/90/100 response.
  - Proportion of subjects achieving SCORAD 50/75/90 response.
  - Change from Baseline in POEM at Weeks 4, 16, 24 and 40.
  - Change from Baseline at Weeks 4, 16, 24 and 40 in MOS Sleep Scale (Sleep Disturbance Score, Snoring Score, Short of Breath Score, Sleep Adequacy Score, Sleep Somnolence Score, Sleep Problems Index 1 Score, Sleep Problems Index 2 Score, Optimal Sleep Score, and Sleep Quantity Score).
  - Change from Baseline at Weeks 16 and 40 in Asthma Symptoms Questionnaire.
  - Change from Baseline at Weeks 16 and 40 in Daytime Nasal Symptoms Questionnaire.
  - Change from Baseline in total sleep time per night (TST min), Sleep Efficiency (%), Wake After Sleep Onset (WASO), number of scratching events per hour, mean activity during rest (sleep) periods as measured by actigraphy, by week until Week 40 and by visit thereafter.
  - Change from Baseline in ADERM-SS and ADERM-IS by week until Week 40 and by visit thereafter.
  - Change from Baseline in PGIS.
  - Proportion of subjects with a DLQI 0 or 1 response.
-

- Change from Baseline in DLQI.
- Change from re-randomization in EASI score in Period 2.

Primary and secondary variables will also be evaluated at all scheduled visits.

The efficacy of rescue will be summarized for subjects who received the rescue medication.

Due to collection issues in DLQI Question 7, the corresponding secondary endpoints have been changed to exploratory variables and the answers to Question 7 will be removed from the analyses. Of note, correction to the DLQI ePRO device has been corrected while the study is ongoing. Additional analyses based on correct DLQI data may be performed.

The EASI overall score, IGA and pruritus NRS score will be summarized at Baseline and Week 16 for subjects from Japan, with the percentage changes in EASI and pruritus NRS from baseline to Week 16.

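### The SAP's visit-window rule has no place for the required 4-week post-topical-rescue EASI, so the rescue summary needs its own time point

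*SAP*

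**What the plan says.** SAP Section 6.0 (Definition of Analysis Windows) bases all time points in each period on days since the first dose in that period. Within a window, "If more than one assessment is included in a time window, the assessment closest to the nominal day will be used"; ties go to the later assessment. Table 7 gives the Period 2 windows for EASI. It has rows for the scheduled visits only.

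Under Protocol Section 5.1, "topical corticosteroid treatment will be permitted at the Week 24 visit and thereafter" for subjects with a second response below EASI 50. SAP Section 4.2 adds that for these subjects "a visit will be required 4 weeks after receiving the rescue therapy". The protocol's schedule of activities lists EASI at that visit and allows ±5 days. Subjects still below EASI 50 at that visit must stop study drug.

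SAP Section 10.5 promises: "The efficacy of rescue will be summarized for subjects who received the rescue medication". It gives no time axis, window or estimator.

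On missing data, SAP Section 10.1.5 says LOCF will "carry forward the most recent previous non-missing value". Protocol Section 8.1.5 refers instead to the previous visit's evaluation. Protocol Section 5.1 also creates a second kind of off-schedule EASI: "Subjects who prematurely discontinue study drug should complete a Premature Discontinuation Visit (PD visit) as soon as possible, preferably within 2 weeks".

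**The concern.** The 4-week visit exists to judge whether topical rescue worked, and its result decides whether the subject stays on study drug. It has no analysis window of its own. Under the general rule it competes with the scheduled visit at which rescue began, and that visit sits on or close to the nominal day.

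If the rescue summary is programmed from the windowed data, the response at 4 weeks disappears. The first post-rescue value is then the next scheduled visit, 8 weeks after rescue (from Week 24 or 32) or 12 weeks after (from Week 40 to 76). Subjects who failed at 4 weeks and stay in follow-up contribute an off-drug value there, mixed with on-drug values from those who responded.

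Premature-discontinuation (PD) visits raise a smaller question of the same kind: whether an EASI that no window selects may still be carried forward.

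**Working it through.** **Reproducing the windows.** The boundary between two visits is the midpoint of their nominal days, with the midpoint day given to the earlier visit, as in the SAP's example: "the split between Week 2 and Week 4 would be between P1 Rx Days 22 and 23". (The rule as worded, "the threshold is determined as being between that Rx day and the Rx day prior to it", would put that split at 21/22. The tables follow the example.)

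- Table 2, nominal days 15, 29, 57, 85, 113: midpoints 22, 43, 71, 99. All bounds match.
- Table 7, nominal days 29, 57, 113, 169, 253, 337, 421, 505: midpoints 43, 85, 141, 211, 295, 379, 463. All bounds match except two. Week 40 should start at 142 (printed 156), leaving Days 142–155 uncovered. Week 76 should start at 380 (printed 378), an overlap at Days 378–379.

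**Where the 4-week visit falls.** Assume topical treatment starts on the day of a scheduled visit. Nominal day of the 4-week visit = rescue visit day + 28.

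| Rescue visit | Rescue day | 4-week day | Range with tolerances | Table 7 window of rescue visit |
|---|---|---|---|---|
| Week 24 | 57 | 85 | 75–95 | 44–85 |
| Week 32 | 113 | 141 | 131–151 | 86–141 |
| Week 40 | 169 | 197 | 187–207 | 156–211 |
| Week 52 | 253 | 281 | 271–291 | 212–295 |
| Week 64 | 337 | 365 | 355–375 | 296–379 |
| Week 76 | 421 | 449 | 439–459 | 378–463 |

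The range allows ±5 days on the rescue visit and ±5 on the 4-week visit, so ±10 in total.

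**Who wins the window.** In the rescue visit's own window, the 4-week visit is at least 28 − 10 = 18 days from nominal, and the rescue visit is at most 5. The only spill into another printed window is after Week 24 rescue, on Days 86–95. These are 18 to 27 days from Week 32's nominal Day 113, and the attended Week 32 visit is at most 5 days from it. So the 4-week visit is selected for 0 of 6 rescue timings. Correcting the two Table 7 bounds leaves this at 0 of 6, because the margin of 18 days against 5 is unchanged.

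**The gap.** After Week 32 rescue, the 4-week visit falls on Day 142 or later when the two deviations sum to at least +1. Of 11 × 11 = 121 combinations, 11 sum to zero and the rest split evenly: (121 − 11)/2 = 55, and 55/121 = 45%. Under Table 7 as printed these assessments belong to no window.

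**Exception.** If Week 32 is missed after Week 24 rescue, the 4-week visit is selected when it falls on Day 86 or later, again 55/121 = 45%. With the bounds corrected, the same holds for a missed Week 40 after Week 32 rescue.

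**PD visits in Period 1.** With scheduled visits on nominal days, a PD visit falls in a window already filled by a nearer visit on Days 16–22, 30–43, 58–71 and 86–99: 7 + 14 + 14 + 14 = 49 days. Days 2–112 contain 111 − 4 = 107 non-visit days, and 49/107 = 46%. Simulated with the ±3-day tolerance, the share is 39%. The value used instead is about 14 days older at most.

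**Size if LOCF were limited to window-selected values.** Change in the drug–placebo difference ≈ (difference in proportions leaving) × 0.458 × (worsening at the PD visit). The inputs are assumed; the protocol's sample-size section states no dropout rate.

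- Placebo 15%, 30 mg 5%, worsening 20 points: 0.10 × 0.458 × 20 = 0.9 points.
- Placebo 30%, 30 mg 10%, worsening 40 points: 0.20 × 0.458 × 40 = 3.7 points.
- No worsening: 0.

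The planned difference is 70 − 35 = 35 points. With more dropout on placebo, leaving out the PD scores makes the difference smaller.

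**The case against.** The strongest reply is that nothing ties the rescue summary to Table 7. SAP 10.5 leaves it open, and SAP 10.1.5 separately removes post-rescue efficacy data from the NRI, LOCF and as-observed analyses, so the window rule costs those analyses nothing. The summary is exploratory and descriptive. All of this stands, and it makes the consequence conditional. It does not remove the gap. Section 6.0 claims all time points, Table 7 is the only Period 2 EASI scheme, and the rescue summary is the one named analysis whose subject is post-rescue data.

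A reader might also infer that the primary Week 16 analysis loses the last EASI before dropout in nearly half of discontinuations. The documents do not support that. Read literally, the LOCF wording in SAP 10.1.5 carries the PD score forward whether or not a window selected it. Subjects who stop study drug are to be followed at all scheduled visits, so those who stay have an observed Week 16 EASI. The 39–46% applies only to subjects who leave the study, and assumes PD visits spread evenly over the period. Multiple imputation does work from by-visit values and could omit such a score, but it is a sensitivity analysis.

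**Conclusion.** The concern holds for the rescue summary. As written or with its bounds corrected, Table 7 does not select the 4-week post-topical-rescue EASI for rescue at any visit from Week 24 to Week 76, provided rescue starts at a scheduled visit and scheduled visits are attended. Whether this distorts a reported result depends on whether the summary is built from these windows, which the SAP leaves unstated.

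For LOCF, the finding is only that one clarifying sentence is needed. The protocol and SAP describe the carried value differently, and neither says whether an unselected assessment qualifies. On the literal SAP reading nothing is lost. On the narrower reading the effect depends wholly on assumed dropout and worsening, and is nil if PD scores do not worsen.

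**What to change.** 1. In SAP Sections 6.0 and 10.5, give the rescue summary its own time point counted from the first topical dose (nominal day 29), and state that it uses the 4-week post-rescue assessment.
2. Correct the Table 7 lower bounds for Week 40 (142) and Week 76 (380), and align the wording of the split rule with its example.
3. In SAP Section 10.1.5, state that LOCF carries forward the last non-missing assessment by date within the period, including PD assessments not selected for a window.

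I would not move PD scores to the next scheduled visit for multiple imputation. That would enter them as observed later-visit values, and could collide with real follow-up data in subjects who continue visits.

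The cost is a few sentences and a small programming change. The EASI is already scheduled at these visits, so no new data are needed.
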